6.5.1.2 Follow-up for QT prolongation

[figure not shown]
In the event that QT prolongation is detected during routine investigation, the following guidance is provided to be followed by the investigator:

- If a QTcF > 480 msec is observed or an increase of the QTcF of > 60 msec compared to baseline QTcF assessment of the roll-over, then two additional ECGs, each 2-3 minutes apart, need to be taken after the initial ECG. The mean QTcF from the triplicate ECGs will be determined. If the mean QTcF is > 480 msec or the mean QTcF increase is > 60 msec compared to baseline, the patient has to interrupt study treatment while an urgent cardiology

consultation is obtained to re-evaluate the ECG and perform a clinical consultation. If immediate treatment is required for subject safety, this should be initiated at the study site without delay and without waiting for confirmation by a cardiologist.

Based on the cardiologist consultation, the following should occur:

- If a mean QTcF > 480 msec is NOT confirmed, no further action needs to be taken.
- If the cardiologist confirms a mean QTcF > 500 msec, the subject has to discontinue according to the discontinuation procedure described in [Section 9.1.1](#). The subject must remain under observation until the QTcF is < 480 msec and serum electrolytes, calcium, and magnesium are measured and the results normal. This observation may be done at the site, in an Emergency Room, or a cardiology clinic, as appropriate and depending upon local resources.
- If the cardiologist confirms that QTcF > 480 msec, osilodrostat treatment is temporarily interrupted and a thorough evaluation is performed to assess the patient for acute cardiovascular risk, and for possible underlying heart disease that needs additional evaluation and management.
 - a. If based upon the assessment by the cardiologist, the investigator considers that there is an acute cardiovascular safety risk and that the patient should not continue with study medication, the patient needs to be discontinued immediately (discontinuation criteria described in [Section 9.1.1](#)).
 - b. If based upon the assessment by the cardiologist, the investigator considers that there is not an acute cardiovascular safety risk; the patient can continue to receive study medication.

Figure 6-1 QT monitoring Flow Chart

* Please refer to [Section 9.1.1](#), study treatment must be discontinued under this circumstance.

6.5.2 Follow-up for toxicities

Please refer to [Section 6.5.1](#).

6.5.3 Follow up for potential drug-induced liver injury (DILI) cases

In the event that concomitant aminotransferase and bilirubin elevations are detected during routine investigation, the following guidance is provided to be followed by the investigator.

Patients with transaminase increase combined with TBIL increase may be indicative of potential DILI, and should be considered as clinically important events.

The threshold for potential DILI may depend on the patient's baseline AST/ALT and TBIL value; patients meeting any of the following criteria will require further follow-up as outlined below:

- For patients with normal ALT and AST and TBIL value at baseline: AST or ALT $> 3.0 \times$ ULN combined with TBIL $> 2.0 \times$ ULN
- For patients with elevated AST or ALT or TBIL value at baseline: [AST or ALT $> 2 \times$ baseline AND $> 3.0 \times$ ULN] OR [AST or ALT $> 8.0 \times$ ULN], combined with [TBIL $> 2 \times$ baseline AND $> 2.0 \times$ ULN]

Medical review needs to ensure that liver test elevations are not caused by cholestasis, defined as ALP elevation $> 2.0 \times$ ULN with R value < 2 in patients without bone metastasis, or elevation of ALP liver fraction in patients with bone metastasis.

In the absence of cholestasis, these patients should be immediately discontinued from study drug treatment, and repeat LFT testing as soon as possible, preferably within 48 hours from the awareness of the abnormal results. The evaluation should include laboratory evaluations, detailed history, physical assessment and the possibility of liver metastasis or new liver lesions, obstructions/compressions, etc.

1. Laboratory evaluations should include ALT, AST, albumin, creatine kinase, total bilirubin, direct and indirect bilirubin, GGT, prothrombin time (PT)/INR and alkaline phosphatase.
2. A detailed history, including relevant information, such as review of ethanol, concomitant medications, herbal remedies, supplement consumption, history of any pre-existing liver conditions or risk factors, should be collected.
3. Further testing for acute hepatitis A, B, C or E infection and liver imaging (e.g. biliary tract) may be warranted.
4. Obtain PK sample, as close as possible to last dose of study drug, if PK analysis is performed in the study.
5. Additional testing for other hepatotropic viral infection (CMV, EBV or HSV), autoimmune hepatitis or liver biopsy may be considered as clinically indicated or after consultation with specialist/hepatologist.

All cases confirmed on repeat testing meeting the laboratory criteria defined above, with no other alternative cause for LFT abnormalities identified should be considered as "medically significant", thus, met the definition of SAE ([Section 10.1.2](#)) and reported as SAE using the term "potential drug-induced liver injury". All events should be followed up with the outcome clearly documented.

6.6 Additional treatment guidance

6.6.1 Treatment compliance

The investigator must promote compliance by instructing the subject to take the study treatment exactly as prescribed and by stating that compliance is necessary for the subject's safety and the validity of the study. The subject must also be instructed to contact the investigator if he/she is unable for any reason to take the study treatment as prescribed. Compliance will be assessed by the investigator and/or study personnel at each visit using pill counts (if applicable) and information provided by the subject. This information should be captured in the source

document at each visit. All study treatment dispensed and returned must be recorded in the Drug Accountability Log.

6.6.2 Emergency breaking of assigned treatment code

Not applicable.

6.7 Preparation and dispensation

Each study site will be supplied with study drug in packaging as described under investigational and control drugs section.

Investigator staff will identify the study medication kits to dispense to the subject by contacting the IRT and obtaining the medication number(s). The study medication has a 2-part label (base plus tear-off label), immediately before dispensing the medication kit to the subject, site personnel will detach the outer part of the label from the packaging and affix it to the source document.

6.7.1 Handling of study treatment

Study treatment must be received by a designated person at the study site, handled and stored safely and properly and kept in a secured location to which only the investigator and designated site personnel have access. Upon receipt, all study treatment must be stored according to the instructions specified on the labels and in the [Investigator's Brochure]. Clinical supplies are to be dispensed only in accordance with the protocol. Technical complaints are to be reported to Recordati Quality Assurance.

The investigator must maintain an accurate record of the shipment and dispensing of study treatment in a drug accountability log. Monitoring of drug accountability will be performed by monitors during site visits or remotely and at the completion of the trial. Subjects will be asked to return all unused study treatment and packaging at the end of the study or at the time of discontinuation of study treatment.

At the conclusion of the study, and as appropriate during the course of the study, the investigator will return all unused study treatment, packaging, drug labels, and a copy of the completed drug accountability log to the CRO monitor or to the address provided by Recordati or the CRO in the investigator folder at each site.

7 Informed consent procedures

Eligible subjects may only be included in the study after providing (witnessed, where required by law or regulation), IRB/IEC-approved informed consent.

If applicable, in cases where the subject's representative(s) gives consent (if allowed according to local requirements), the subject must be informed about the study to the extent possible given his/her understanding. If the subject is capable of doing so, he/she must indicate agreement by personally signing and dating the written informed consent document.

Informed consent must be obtained before conducting any study-specific procedures (e.g. all of the procedures described in the protocol). The process of obtaining informed consent must be documented in the subject source documents.

CRO on behalf of Recordati will provide to investigators in a separate document a proposed informed consent form that complies with the ICH GCP guidelines and regulatory requirements and is considered appropriate for this study. Any changes to the proposed consent form suggested by the investigator must be agreed by Recordati before submission to the IRB/IEC.

Information about common side effects already known about the investigational drug can be found in the Investigator's Brochure (IB). This information will be included in the subject informed consent and should be discussed with the subject during the study as needed. Any new information regarding the safety profile of the investigational drug that is identified between IB updates will be communicated as appropriate, for example, via an investigator notification or an aggregate safety finding. New information might require an update to the informed consent and then must be discussed with the subject.

Women of child bearing potential must be informed that taking the study treatment may involve unknown risks to the fetus if pregnancy were to occur during the study and agree that in order to participate in the study they must adhere to the contraception requirements.

A copy of the approved version of all consent forms must be provided to the sponsor after IRB/IEC approval.

8 Visit schedule and assessments

Assessment schedule lists all of the assessments when they are performed. All data obtained from these assessments must be supported in the subject's source documentation.

Subjects should be seen for all visits/assessments as outlined in the assessment schedule or as close to the designated day/time as possible. Missed or rescheduled visits should not lead to automatic discontinuation. Subjects who prematurely discontinue the study for any reason should be scheduled for a visit as soon as possible, at which time all of the assessments listed for the final visit will be performed. At this final visit, all dispensed investigational product should be reconciled, and the adverse event recorded on the CRF.

Table 8-1 Assessment Schedule

Visit Name	Category	Protocol Section	Baseline / Enrollment	Visits during Treatment (Week 12 and every 12 weeks (+/- 2 weeks) thereafter)					End of study treatment (EoT)	30 day safety follow-up post last dose of study drug / End of Study	
			W1D1	W12D1	W24D1	W36D1	W48D1	W60D1 Onwards			
Visit Number			1	110	120	130	140	150	1999	FU	
Obtain informed consent	D	7	x								
Study History	D	8.2	x								
Demography	D	8.2	x								
Medical History	D	8.2	x								
Inclusion/exclusion criteria	D	5.1	x								
Blood chemistry	D	8.4.3	x		x		x		x	x	
Hematology	D	8.4.3	x		x		x		x	x	
Physical examination	S	8.4.1	x	x	x	x	x	x	x	x	
Body weight / blood pressure	D	8.4.2	x	x	x	x	x	x	x	x	
UFC (two 24-h specimens)	D	8.4.3	x	x	x	x	x	x	x	x	
Plasma ACTH	D	8.4.3	x	x	x	x	x	x	x	x	
11-deoxycortisol and 11 deoxycorticosterone, testosterone	D	8.4.3	x		x		x		x	x	
12 Lead safety ECG assessment	D	8.4.4	x		x		x		x	x	
Pituitary MRI	D	8.4.6	x				x		x		
Urine pregnancy testing (if positive, serum pregnancy test required) – WOCBP only	S	8.4.5	x	At every visit and monthly (at home)					x	x	
Adverse events and Serious adverse events	D	10.1	x	continuous							
Osilodrostat drug administration record	D	6.1	x	continuous							

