4.5 Risks and benefits

There is still an unmet need in the treatment of CD: despite available therapies, a substantial number of subjects do not achieve normalization of cortisol, lose biochemical control over time or present medication-related adverse reactions and may stop treatment because of this.

In order to mitigate the potential risks related to the administration of osilodrostat, some procedures will be taking place:

- The starting dose should be the same as the dose provided in the parent osilodrostat study at the time of transition to the roll-over study. However, the investigator can change the dose based on the subject's response; the maximal dose should not exceed 30 mg b.i.d.
- Subjects will be evaluated by the treating investigator for clinical benefit and safety based on the following assessments:
 - Physical examination (every 12 weeks)
 - Body weight / blood pressure (every 12 weeks), 12-lead safety ECG (every 24 weeks), blood chemistry and hematology (every 24 weeks), 11-deoxycortisol and 11 deoxycorticosterone (every 24 weeks), testosterone (every 24 weeks), Urinary Free Cortisol (UFC) (every 12 weeks), serum cortisol as clinically indicated, plasma ACTH (every 12 weeks) and pituitary MRI (every 48 weeks or more frequently if clinically needed).
- AEs and SAEs will be reported continuously and evaluated by the investigator at each visit.
- Drug administration record for dosing of osilodrostat will be completed at baseline and during treatment visits.
- For females, urinary pregnancy test will be performed at each visit (every 12 weeks) and monthly, at home.
- Upon administration of the last drug dose, discontinuation from the study or study end, the patient will have a follow-up visit 30 days later.
- The protocol provides specific guidance for dose modifications and/or stopping rules, due to osilodrostat-related toxicities. In addition, a safety follow-up for liver toxicity and management of QT prolongation have also been included.

Potential subject benefits

There is an unmet medical need in subjects with CS since this is a rare and serious disease but with limited medical treatment options.

An open label, proof-of-concept, single-arm study (CLCI699C2201, LINC 2) has been conducted to assess the safety and tolerability of osilodrostat in patients with CD after 10 weeks of treatment.

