8.4.3 Laboratory evaluations

All laboratory evaluations will be performed using central laboratory according to the Assessment schedule: blood chemistry (Albumin, alkaline phosphatase, total bilirubin, calcium, creatinine, CK, GGT, inorganic phosphorus, lipase, amylase, magnesium, potassium, total protein, AST, ALT, sodium, urea/BUN and uric acid, HbA1c), hematology (Hemoglobin, hematocrit, red blood cell count, white blood cell count with differential, (monocytes, eosinophils, basophils, neutrophils, lymphocytes), and platelet count), testosterone, serum cortisol as clinically indicated, urine free cortisol (two 24-hour urine specimens collected), plasma ACTH, 11-deoxycortisol and 11 deoxycorticosterone.

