8.4.4 Electrocardiogram (ECG)

Twelve-lead safety ECGs are collected at the study site using ECG equipment available at the sites. This ECG must be read on site by a qualified physician (e.g., the investigator, or another qualified physician such as a consulting cardiologist) on the day they are collected and recorded in eCRF for each patient.

Only ECGs with clinically significant ("notable") abnormalities should be reported as AE. A "notable abnormality" is defined as:

- QTcF > 480msec with acute cardiovascular risk, as assessed by a consulting cardiologist
- Any QTcF > 500msec, confirmed by a consulting cardiologist

- QTcF increase > 60 msec from baseline.

The frequency of the ECG assessment is provided in [Table 8-1](#).

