8.4.6 Pituitary scan

Pituitary MRI scanning with gadolinium enhancement will be performed every 48 weeks or more frequently if clinically needed at visits according to the assessment schedule provided in [Table 8-1](#) using the local site facility. These will be assessed locally to determine the longest diameter and the tumor volume. For MRI (or CT) images that are not interpretable for tumor volume, the longest dimension (in mm) will be summarized instead. If MRI intravenous contrast is contraindicated for a patient, a non-contrast MRI scan should be performed. If MRI cannot be performed at all then a CT (with i.v. contrast if not contraindicated) may be performed. Digital images are to be kept at the site in the event Recordati requests transfer of the files at a later date. The Pituitary MRI scanning should be recorded in eCRF.

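### Table 8-1 marks no routine laboratory test or ECG between week 48 and end of treatment, although protocol section 4.5 sets a 24-week cycle with no end

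*Protocol*

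**What the plan says.** Protocol section 8 introduces Table 8-1 with the statement "Assessment schedule lists all of the assessments when they are performed". The treatment columns are W12, W24, W36, W48 and a last one headed "W60D1 Onwards", which serves all later 12-weekly visits.

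- **Marked in the last column:** physical examination, body weight and blood pressure, UFC, plasma ACTH.
- **Blank in the last column:** blood chemistry; hematology; 11-deoxycortisol, 11-deoxycorticosterone and testosterone; the row "12 Lead safety ECG assessment"; pituitary MRI. Apart from MRI, these rows are marked at baseline, W24, W48, end of treatment (EoT) and the 30-day follow-up. MRI is marked at baseline, W48 and EoT.

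Section 4.5 gives intervals without an end point: "12-lead safety ECG (every 24 weeks), blood chemistry and hematology (every 24 weeks"), and "11-deoxycortisol and 11 deoxycorticosterone (every 24 weeks), testosterone (every 24 weeks"). The sections on the individual assessments give no laboratory or ECG interval of their own. Section 8.4.3 reads "All laboratory evaluations will be performed using central laboratory according to the Assessment schedule". Section 8.4.4 reads "The frequency of the ECG assessment is provided in" Table 8-1. MRI differs, because section 8.4.6 has its own interval: "Pituitary MRI scanning with gadolinium enhancement will be performed every 48 weeks or more frequently if clinically needed".

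On the end of follow-up, section 4.5 and Table 8-1 describe a visit 30 days after the last dose, with laboratory tests and ECG marked in the table. Section 9.2 describes a telephone call at that time.

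**The concern.** A blank is correct for week 60 itself, which is not a multiple of 24. The same cell also stands for W72, W96, W120 and so on, when section 4.5 makes laboratory tests and ECG due. No footnote bridges the two, and the 24-week interval appears only in the risk-benefit rationale, not in the sections that tell sites what to do.

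This matters mainly for patient safety. Section 9.1.1 requires treatment to stop for confirmed potassium or sodium abnormalities, for combined transaminase and bilirubin elevation, and for confirmed QTcF above 500 msec. The QT guidance in 6.5.1.2 and the liver guidance in 6.5.3 both begin with a finding on routine investigation. A silent electrolyte or QTcF change is found only by testing. The Amendment 01 rationale says that Health Authorities had asked for safety monitoring to be specified, and Table 8-1 is where sites read it.

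There is also a cost to the data. Laboratory and ECG results are a secondary safety endpoint (Protocol Table 2-1). SAP 7.4.2 and 7.4.4 summarise them by the worst on-treatment value and by notable values at any post-baseline time. Fewer tests give fewer chances to see an abnormality.

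**Working it through.** The plan states no figure to reproduce. The check compares the marks in Table 8-1 with the visits that section 4.5 makes due.

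**Inputs**
- Treatment visits every 12 weeks; laboratory and ECG marks on treatment at W24 and W48 only (Table 8-1).
- Laboratory tests and ECG every 24 weeks (section 4.5).
- Study open about 5 years from first patient first visit (section 3.1), taken as a ceiling for one patient.
- Individual treatment durations are not given, so a range is shown.

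**Extraction check.** The assessment rows of the table have equal numbers of fields, and the last treatment column is filled in the four 12-weekly rows. The blanks are therefore unlikely to come from reading the PDF.

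**Formulas**
- Weeks on treatment = years × 365.25 / 7.
- Due points = number of multiples of 24 up to that week.
- Unmarked points = due points − 2 (W24 and W48 are marked).
- Gap = weeks on treatment − 48.
- Scheduled post-baseline values for a patient treated past W48: literal table = W24 + W48 + EoT + follow-up = 4; under 4.5 = due points + 2.

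| Years on treatment | Weeks | Due | Unmarked | Gap W48 to EoT (weeks) | Scheduled values: literal vs 4.5 |
|---|---|---|---|---|---|
| 1 | 52.2 | 2 | 0 | 4.2 | 4 vs 4 |
| 1.5 | 78.3 | 3 | 1 (W72) | 30.3 | 4 vs 5 |
| 2 | 104.4 | 4 | 2 (W72, W96) | 56.4 | 4 vs 6 |
| 3 | 156.5 | 6 | 4 (W72 to W144) | 108.5 | 4 vs 8 |
| 5 | 260.9 | 10 | 8 (W72 to W240) | 212.9 | 4 vs 12 |

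The intended gap is 24 weeks. The literal count of 4 holds only for patients who pass W48. A patient leaving before W24 has 2 values (EoT and follow-up), and one leaving between W24 and W48 has 3. The two readings do not differ for those patients.

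**Is long treatment plausible?** The amendment rationales report 23 patients enrolled by 29 January 2019 and 100 by 8 April 2020. SAP version 3.2 is dated 26 June 2023 and still allows for further interim analyses. Patients enrolled by those two dates and still treated at the SAP date would have at least 1609 / 7 = 229.9 and 1174 / 7 = 167.7 weeks. That gives at least 9 − 2 = 7 of 9 and 6 − 2 = 4 of 6 points unmarked. These are potential durations, not observed ones.

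**The case against.** The strongest reply is that the table is incomplete and does not contradict 4.5. Its marks from W12 to W60 fit the 24- and 48-week cycles. One column cannot show a 24-weekly item across 12-weekly visits, and a plain mark there would have asked for laboratory tests twice as often as 4.5 does. Section 4.5 supplies the interval, and a careful site would infer it. This stands in part: a reader might infer that laboratory tests and ECGs were meant to stop at week 48, and the documents do not support that. It does not remove the problem, because the operative sections send sites to a table with no repeat rule.

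Other stronger readings also fail.

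- **MRI is lost after week 48.** Section 8.4.6 gives the 48-week interval, so only the cell needs tidying.
- **The SAP tables rest on scheduled values alone.** SAP 7.4.2 takes all available laboratory assessments from all sources up to 30 days after the last dose, and 7.4.4 counts notable QTcF at any post-baseline time. For-cause and unscheduled laboratory tests therefore count. What is thinned is routine testing.
- **Five-year patients are typical.** Five years runs from the first patient's first visit. Patients leave when the drug is commercially available (9.1.1), and the EU and US approvals date from early 2020. The 8 of 10 figure is a ceiling.
- **Safety monitoring lapses altogether.** Blood pressure, physical examination, UFC and ACTH stay marked. Adverse events are collected throughout, including clinically significant laboratory results and notable QTcF, and section 14 provides for extra safety tests case by case. These are real but partial safeguards, because they do not prompt a routine test in a patient without symptoms.

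**Conclusion.** The point holds as a conflict between a schedule that governs and an interval stated elsewhere, and it should be fixed. Its size depends on how sites read the table. Under a literal reading, half of the due laboratory and ECG points are unmarked at 2 years, two thirds at 3 years and at most four fifths at 5 years. If sites follow 4.5, the loss is zero. The documents do not show which reading sites used, so no actual data loss is claimed.

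The consequence is weaker routine detection of the laboratory and QTcF stopping criteria and sparser secondary safety data. The primary endpoint, frequency and severity of adverse events, is touched only indirectly, through abnormalities that would have been reported as events had they been found. The call in 9.2 is a smaller inconsistency of the same kind: a call cannot supply the laboratory tests and ECG that Table 8-1 marks at that time.

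**What to change.** In Table 8-1, split the last treatment column or add a footnote: chemistry, hematology, precursors with testosterone, and ECG continue every 24 weeks (W72, W96 and so on), and pituitary MRI every 48 weeks (W96, W144 and so on), until EoT. In section 9.2, replace the 30-day call with the 30-day visit, including laboratory tests and ECG, as in 4.5 and Table 8-1.

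The cost is a small protocol amendment. It adds no testing beyond what 4.5 and Table 8-1 already intend, and it needs no change to the SAP. Where sites did follow the table literally, past gaps cannot be recovered.
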